3 HYPOTHESES AND DECISION RULES

N/A

4 ANALYSIS SETS/POPULATIONS

4.1 FULL ANALYSIS SET

Subjects who newly initiated antidepressant therapies between Jan 01, 2018 to Jun 30, 2019 in the Health Insurance Review and Service (HIRA) database

** Index date is the first prescription date of study drugs, including SSRIs, SNRIs, and other ADs during the intake period (Jan 01, 2018 to Jun 30, 2019).*

Inclusion criteria

Patients must meet all of the following inclusion criteria to be eligible for inclusion in the study:

1. *Patients aged 18 years or older and 70 years or younger on the index date*
2. *Patients who had at least one inpatient claim or two outpatient claims in the intake period with any of the following diagnosis codes:*

PFIZER CONFIDENTIAL

Table 1. Diagnosis Codes for Inclusion

KCD-7 Code ¹⁾	Description
F06.3	Organic mood[affective] disorders
F32*	Depressive episode
F33*	Recurrent depressive disorder
F34.1	Neurotic depression
F38.1	Other recurrent mood[affective] disorders
F41.2	Mixed anxiety and depressive disorder

1) KCD-7 = Korean version of ICD-10

3. Patients prescribed any of the following antidepressant during intake period (from January 1, 2018 to June 30, 2019)

Table 2. Study Drug List

Active Ingredient	Dosage	HIRA Drug Main Ingredient Codes
Escitalopram	5mg	474801ATB
	10mg	474802ATB
	20mg	474803ATB
	15mg	474804ATB
	10mg	521101ATD
	20mg	521102ATD
Paroxetine	10mg	209301ATB
	20mg	209302ATB
	12.5mg	209304ATR
	25mg	209305ATR
Fluoxetine	10mg	161501ACH
	10mg	161501ATB
	20mg	161502ACH
	20mg	161502ATB
	20mg	161502ATD
Mirtazapine	15mg	196201ATB
	15mg	196201ATD
	30mg	196202ATB
	30mg	196202ATD
	7.5mg	196204ATB
	7.5mg	196204ATD
Duloxetine	30mg	495501ACE
	30mg	495501ATE
	60mg	495502ACE
	60mg	495502ATE
Sertraline	50mg	227001ATB
	0.1g	227002ATB
Venlafaxine	75mg	247502ACR
	37.5mg	247504ACR
Tianeptine	12.5mg	229601ATB
Vortioxetine	5mg	628501ATB
	10mg	628502ATB
	15mg	628503ATB

PFIZER CONFIDENTIAL

	20mg	628504ATB
Desvenlafaxine	50mg 100mg	626401ATR 626402ATR
Bupropion	0.1g 0.15g 0.3g	428101ATB 428102ATR 428103ATR

Exclusion criteria

1. Patients meeting any of the following criteria will not be included in the study:
2. Patients with a claim of diagnosis codes in Table 1 during the 12 month pre-index period
3. Patients with a claim of prescription in Table 2 during the 12 month pre-index period
4. Patient who had a claim as a beneficiary of Medical Aid program (Korean Medicaid program with free or minimum copay)
5. Patients who are hospitalized at the index date
6. Patients who are under hospice care (procedure codes WG*-WO*)

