9.7. Data analysis

The proportions and drug utilization patterns comparisons of 11 study drugs will use all the patients satisfying inclusion and exclusion criteria (raw data). Adherence, persistence, discontinuation, recurrence, and adverse outcomes comparison of 11 study drugs will use both raw data and matched data where patients will be matched on demographic and clinical characteristics. All outcome variables will be summarized *descriptively* through the tabular and graphical display of mean values, medians, ranges and standard deviations of continuous variables of interest and frequency distributions of categorical variables. Safety outcomes of treatments will be estimated from time-to-event models. The 95% confidence intervals for the estimates will be calculated and $p < 0.05$ will be considered significant. All analyses will be carried out using SAS version 9.4 which is installed on HIRA server. Analysis and reporting will be compliant with Strengthening the Reporting of Observational Studies in Epidemiology (STROBE) recommendations.

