5.1 EFFICACY/EFFECTIVENESS ENDPOINT(S)

Medication compliance (persistence, discontinuation, adherence) along with recurrence are main primary efficacy endpoints and they are defined as follows:

1. MPR (medication possession ratio)
For each of 11 study drugs, the MPR will be calculated by (Days of medication possession from the prescriptions filled in the 180 days) / (180 days + extra days of drug supply from the last prescription fill during the 180 days)
2. Persistence
For each of 11 study drugs, the average length of treatment on the index drug during the first 180 day period (allowing 14 day permissible gap) will be

PFIZER CONFIDENTIAL

calculated. Switching, combination, augmentation, discontinuation will terminate the persistent period.

3. Discontinuation

For each of 11 study drugs chosen as index drug, the percentage of discontinuation in the first 90 days from the index date (acute treatment phase) will be measured (allowing 14 day permissible gap)

4. Adherence

For each of 11 study drugs chosen as index drug, adherence will be measured by MPR and persistence during the first 90 day and 180 day from the index date, respectively (acute treatment phase). MPR ≥ 0.75 and persistence ≥ 90 will be considered as adherence.

* For those period with any identified adverse outcome such as GI bleeding will be considered as a non-adherent period.

5. Recurrence

Recurrence during the acute treatment phase was operationally defined as either one of the following being satisfied:

- 1) Inpatient episode with a diagnosis code in Table 1
- 2) Inpatient episodes via the department of psychiatry or emergency medicine
- 3) Inpatient episode via nursing hospital
- 4) Emergency room visit with a diagnosis code in Table 1
- 5) Suicide attempt identified by the following KCD-7 codes:
 - T40 Poisoning by narcotics and psychodysleptics [hallucinogens]
 - T41 Poisoning by anaesthetics and therapeutic gases
 - T42 Poisoning by antiepileptic, sedative-hypnotic and antiparkinsonism drugs
 - T43 Poisoning by psychotropic drugs, not elsewhere classified
 - T54 Toxic effect of corrosive substances
 - T60 Toxic effect of pesticides
 - X60-X84 intentional self harm
- 6) Augmentation of the following non-AD drugs
 - Antipsychotic: amisulpride, aripiprazole, olanzapine, quetiapine, risperidone, perphenazine
 - Anticonvulsant: carbamazepine, valproic acid, lamotrigine
 - Mood stabilizer: lithium
 - Anxiolytic: buspirone
 - Thyroid hormone: levothyroxine, liothyronine

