Persistence	Primary outcome	HIRA Database	
For each of 11 study drugs, the average length of treatment on the index drug during the first 180 day period (allowing 14 day permissible gap) will be calculated
 
Switching, combination, augmentation, discontinuation will terminate the persistent period

Discontinuation	Primary outcome	HIRA Database	For each of 11 study drugs chosen as index drug, the percentage of discontinuation in the first 90 days from the index date (acute treatment phase) will be measured (allowing 14 day permissible gap)
Adherence	Primary outcome	HIRA Database	
For each of 11 study drugs chosen as index drug, adherence will be measured by MPR and persistence during the first 90 day and 180 day period from the index date, respectively (acute treatment phase). MPR ≥ 0.75 and persistence ≥ 90 will be considered as adherence.
 
* For those period with any identified adverse outcome such as GI bleeding will be considered as non-adherent period

Drug utilization pattern in acute phase	Secondary outcome	HIRA Database	
During the first 90 day period starting from the index date, the following types of drug utilization pattern is recorded
 
- monotherapy (kept on the index medication)- switching (switched to other antidepressant)- combination (adding other antidepressant)- augmentation (adding other non-AD drug such as antipsychotic)
Drug utilization pattern in maintenance phase	Secondary outcome	HIRA Database	
During the second 90 day period (91 ~ 180 days) starting from the index date, the following types of drug utilization pattern is recorded
 
- choice of antidepressant- monotherapy (kept on the same medication)- switching (switched to other antidepressant)- combination (adding other antidepressant)- augmentation (adding other non-AD drug such as antipsychotic)

PFIZER CONFIDENTIAL

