7.2.2 Study Drug Analysis in Maintenance Phase

- To understand the top 11 antidepressants usage among the Korean patients with depression in maintenance treatment phase
- Primary analysis
- Endpoints:
 - Choice of study drug
 - Average length of new treatment maintenance
 - Average number of co-medications (e.g., atypical antipsychotics, mood stabilizer, thyroid hormone, psychostimulant) when following changes occur from initial monotherapy: switching, combination, augmentation
 - Medication compliance (adherence, discontinuation, and persistence)
 - Recurrence by each antidepressant, by compliance
 - Risk of adverse events
- Population: patients from the acute treatment phase who started maintenance treatment (after 90 days from the index date)
- Significance on continuous variables will be tested by ANOVA (if equal variance condition satisfied) or Kruskal-Wallis H test (otherwise). Provider specialty and other patient characteristics will be used to fit antidepressant choice by multivariate logistic regression analysis of each study drug choice.
- Covariates: antidepressant class covariates such as SSRIs, SNRIs, and other ADs will be used as grouping variables.
- Missing values will be dropped from the analysis
- The role of this analysis is to provide information on study antidepressants in the maintenance phase of drug therapy for Korean patients with depression.

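### Inclusion criterion 2 is not tied to the index date, so entry usually needs a post-index depression claim and starters who never return are preferentially dropped from the compliance outcomes

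*SAP*

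**What the plan says.** SAP 4.1 defines the index date as the first study-drug prescription between 1 January 2018 and 30 June 2019. Inclusion criterion 2 then asks for "Patients who had at least one inpatient claim or two outpatient claims in the intake period with any of the following diagnosis codes". The window is the calendar intake period, not a period around index. Protocol 9.2.1 has the same criterion with an earlier intake start; I use the SAP dates.

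Two exclusions in SAP 4.1 interact with it: "Patients with a claim of diagnosis codes in Table 1 during the 12 month pre-index period" and "Patients who are hospitalized at the index date".

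SAP 5.1 names persistence, discontinuation (first 90 days), adherence and recurrence as main primary endpoints. The first recurrence item is "1) Inpatient episode with a diagnosis code in Table 1", and it carries over to the period after the acute phase. No text exempts the admission that qualified the patient. SAP 7.2.2 lists "Recurrence by each antidepressant, by compliance" for "patients from the acute treatment phase who started maintenance treatment (after 90 days from the index date". Protocol 9.7 adds: "Adherence, persistence, discontinuation, recurrence, and adverse outcomes comparison of 11 study drugs will use both raw data and matched data".

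Protocol 9.9 gives the reason for the claims rule: to limit inclusion of antidepressant use for other diseases. It does not discuss the timing of the claims. Figure 1 was not available to me in either document; no text gives an index-relative rule.

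**The concern.** A cohort followed from the first prescription should be defined by what is known at that date. Here the washout removes patients with depression claims in the year before index, so the claims that confirm the diagnosis mostly have to come afterwards. Entry then depends on behaviour during follow-up.

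The patient most affected is the one who fills once and never comes back. That is the clearest early discontinuer, yet this patient normally fails criterion 2 and leaves both numerator and denominator of the 90-day discontinuation rate. Persistence and adherence are affected in the opposite direction. The protocol motivates the study partly by low antidepressant adherence in Korea (section 7), so this touches a central question.

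Propensity matching or weighting on pre-index measures (SAP 7.1) cannot bring back patients removed for what happened after index.

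A secondary point concerns recurrence. A patient who qualifies only by a post-index admission meets recurrence item 1 by definition.

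**Working it through.** The plan states no figure on this point, so there is none to reproduce. The check is a calendar count followed by an illustration.

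**1. Where can a qualifying claim fall?** Inputs (SAP 4.1): intake 1 Jan 2018 to 30 Jun 2019; 12-month washout; not hospitalized at index.

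- Possible index dates: 365 + 181 = 546.
- An intake day lies before the washout only for index dates 2 Jan to 30 Jun 2019: 180 dates. For these, a claim more than 12 months before index can also count.
- For the other 546 − 180 = 366 dates (67.0%), no such day exists. A qualifying admission must be post-index. The outpatient route needs at least one post-index claim, unless two claims fall on the index date.

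Counting every pair of index day and permitted claim day:

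| Claim day | Pairs | Share |
|---|---|---|
| After index | 545 × 546 / 2 = 148,785 | 89.8% |
| Index day | 546 | 0.3% |
| More than 12 months before index | 180 × 181 / 2 = 16,290 | 9.8% |
| Total | 165,621 | |

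These are shares of calendar days, not of patients. The documents give no patient counts.

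**2. Time left to qualify.** Post-index days remaining in intake fall from 545 (index 1 Jan 2018) to 0 (index 30 Jun 2019). For index dates 1 Apr to 30 Jun 2019, 91 of 546 (16.7%), 90 days or fewer remain. An early starter who stops and returns many months later is kept and counted as discontinued; a late starter with the same history may not be.

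**3. Illustration for discontinuation (all inputs assumed).** Let D be the true 90-day rate in all starters, q the share dropped, and f the share of dropped patients who discontinued. The rate among those included is (D − f·q)/(1 − q). With D = 50%:

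| q | f = 100% | f = 80% | f = 50% |
|---|---|---|---|
| 10% | 0.40/0.90 = 44.4% | 0.42/0.90 = 46.7% | 50% |
| 20% | 0.30/0.80 = 37.5% | 0.34/0.80 = 42.5% | 50% |
| 30% | 0.20/0.70 = 28.6% | 0.26/0.70 = 37.1% | 50% |

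**4. Illustration for adherence (all inputs assumed).** Let A be true adherence and k the adherence of dropped patients relative to the overall rate. The rate among those included is A(1 − k·q)/(1 − q). I take A = 40%; protocol section 7 cites under 50% for Korean patients, without giving the definition.

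| q | k = 0 | k = 0.5 | k = 1 |
|---|---|---|---|
| 10% | 44.4% | 42.2% | 40% |
| 20% | 50.0% | 45.0% | 40% |
| 30% | 57.1% | 48.6% | 40% |

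**5. Recurrence.** No number is offered, because the relevant comparison is with all starters and the documents give nothing to estimate it. Set side by side, criterion 2 and recurrence item 1 show that an admission-only qualifier with a post-index admission is recurrent by definition.

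**The case against.** The best defence is diagnostic specificity. Protocol 9.9 says codes are sometimes entered to avoid denial of payment, so a single coded visit is weak evidence of depression. Some single-claim starters are therefore meant to be excluded, and a rate in all starters is not automatically the right target. This stands, and it is why the rule should stay for the main cohort. It does not justify leaving the effect unmeasured or undisclosed.

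Nor is every dropped patient a discontinuer: a refill under another diagnosis code would not count towards criterion 2. The second claim need not be prompt or accompany an antidepressant, so some early stoppers are kept. Both points stand and limit the size of the bias.

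A reader might infer that the recurrence results are largely built in by the inclusion rule. The documents do not support that. SAP 7.2.1 lists no recurrence analysis in the acute phase, the objectives in both documents place recurrence in maintenance, and SAP 7.2.2 analyses patients who started maintenance after day 90. Most of them would be expected to have repeat outpatient claims. What remains is that SAP 5.1 defines acute-phase recurrence and protocol 9.7 compares recurrence across drugs without naming a phase.

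A reader might also infer that the drug comparisons are biased. That follows only if the selection differs by drug, and nothing in the documents shows that it does.

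Finally, the study is exploratory and SAP section 3 sets no hypotheses. True, but the absolute rates are themselves a main product, and protocol 9.7 reports them in unmatched data too.

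**Conclusion.** The mechanism follows from the written rules: entry usually needs a depression claim after index, and patients who never return with one in intake are preferentially lost. The likely direction is understated 90-day discontinuation and overstated persistence and adherence, on the assumption that dropped patients discontinue more often than those kept.

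The size is unknown. The tables above show what assumed inputs would produce, from no bias to a large one; they are not estimates for this study. The recurrence effect is secondary and probably small in the SAP 7.2.2 analysis. The point is worth acting on because the remedy is cheap, not because a large error has been shown.

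**What to change.** 1. Keep the one-inpatient or two-outpatient rule for the main cohort.
2. Add a sensitivity cohort defined by a Table 1 code on the index-date claim, with no post-index claim required and the other criteria unchanged. Report discontinuation, persistence, adherence and recurrence in it beside the main results. The gap shows how much the rule matters; neither cohort should be presented as the true one.
3. Report by drug the number of patients who qualify only by a post-index admission. Give recurrence with them included, and again with them removed from both numerator and denominator. Do not keep them in the denominator while deleting their admission: that makes them non-recurrent by construction unless they have another event, and leaves unclear how an emergency visit or self-harm code from the same episode is counted.
4. State that main-cohort compliance rates apply to patients with a confirmed depression diagnosis, most of whom returned after index, and are not rates for all new starters.

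**Cost.** Steps 1 and 4 are wording; step 3 needs a flag and one extra table. Step 2 has lower diagnostic specificity, so it stays a sensitivity analysis. It also needs single-visit patients in the HIRA extract, which the documents do not confirm; the SAP mentions limited data capacity and was amended during data analysis. If they are not in the extract, say so and rely on steps 3 and 4.

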4.2 SAFETY ANALYSIS SET

The safety analysis set is the same as the full analysis set.

4.3 OTHER ANALYSIS SET

N/A

4.4 SUBGROUPS

Subgroup analysis may be considered, including but not limited to subgroup analyses by age (<20, 21-64, >65), gender, comorbidities, and prescribing physician's specialty.

5 ENDPOINTS AND COVARIATES

Endpoints are categorized by primary objectives and secondary objectives.

5.1 EFFICACY/EFFECTIVENESS ENDPOINT(S)

Medication compliance (persistence, discontinuation, adherence) along with recurrence are main primary efficacy endpoints and they are defined as follows:

1. MPR (medication possession ratio)
For each of 11 study drugs, the MPR will be calculated by (Days of medication possession from the prescriptions filled in the 180 days) / (180 days + extra days of drug supply from the last prescription fill during the 180 days)
2. Persistence
For each of 11 study drugs, the average length of treatment on the index drug during the first 180 day period (allowing 14 day permissible gap) will be

PFIZER CONFIDENTIAL

calculated. Switching, combination, augmentation, discontinuation will terminate the persistent period.

3. Discontinuation

For each of 11 study drugs chosen as index drug, the percentage of discontinuation in the first 90 days from the index date (acute treatment phase) will be measured (allowing 14 day permissible gap)

4. Adherence

For each of 11 study drugs chosen as index drug, adherence will be measured by MPR and persistence during the first 90 day and 180 day from the index date, respectively (acute treatment phase). MPR ≥ 0.75 and persistence ≥ 90 will be considered as adherence.

* For those period with any identified adverse outcome such as GI bleeding will be considered as a non-adherent period.

5. Recurrence

Recurrence during the acute treatment phase was operationally defined as either one of the following being satisfied:

- 1) Inpatient episode with a diagnosis code in Table 1
- 2) Inpatient episodes via the department of psychiatry or emergency medicine
- 3) Inpatient episode via nursing hospital
- 4) Emergency room visit with a diagnosis code in Table 1
- 5) Suicide attempt identified by the following KCD-7 codes:
 - T40 Poisoning by narcotics and psychodysleptics [hallucinogens]
 - T41 Poisoning by anaesthetics and therapeutic gases
 - T42 Poisoning by antiepileptic, sedative-hypnotic and antiparkinsonism drugs
 - T43 Poisoning by psychotropic drugs, not elsewhere classified
 - T54 Toxic effect of corrosive substances
 - T60 Toxic effect of pesticides
 - X60-X84 intentional self harm
- 6) Augmentation of the following non-AD drugs
 - Antipsychotic: amisulpride, aripiprazole, olanzapine, quetiapine, risperidone, perphenazine
 - Anticonvulsant: carbamazepine, valproic acid, lamotrigine
 - Mood stabilizer: lithium
 - Anxiolytic: buspirone
 - Thyroid hormone: levothyroxine, liothyronine

Recurrence after the acute treatment phase was operationally defined as either one of the following being satisfied:

- 1) ~6) the same as above
- 7) AD prescription after 30 days of drug holiday

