Adherence	Primary outcome	HIRA Database	
For each of 11 study drugs chosen as index drug, adherence will be measured by MPR during the first 90 days from the index date (acute treatment phase)
 
* MPR = (Days of medication possession from the prescriptions filled in the 90 days) / (90 days + extra days of drug supply from the last prescription fill during the 90 days)
 
** For those period with any identified adverse outcome such as GI bleeding will be considered as

			non-adherent period
Drug utilization pattern in acute phase	Secondary outcome	HIRA Database	
During the first 90 day period starting from the index date, the following types of drug utilization pattern is recorded
 
 - monotherapy (kept on the index medication) - switching (switched to other antidepressant) - combination (adding other antidepressant) - augmentation (adding other non-AD drug such as antipsychotic)
Drug utilization pattern in maintenance phase	Secondary outcome	HIRA Database	
During the second 90 day period (91 ~ 180 days) starting from the index date, the following types of drug utilization pattern is recorded
 
 - choice of antidepressant - monotherapy (kept on the same medication) - switching (switched to other antidepressant) - combination (adding other antidepressant) - augmentation (adding other non-AD drug such as antipsychotic)
Recurrence	Primary outcome	HIRA Database	
Recurrence was operationally defined as either one of the following was satisfied:
 
 1) inpatient episode with a diagnosis code in Table 1 2) emergency room visit with a diagnosis code in Table 1 3) suicide attempt identified by the following KCD-7 codes: 
T40 Poisoning by narcotics and psychodysleptics [hallucinogens] T41 Poisoning by anaesthetics and

PFIZER CONFIDENTIAL

			
therapeutic gases
 
T42 Poisoning by antiepileptic, sedative-hypnotic and antiparkinsonism drugs
 
T43 Poisoning by psychotropic drugs, not elsewhere classified
 
T54 Toxic effect of corrosive substances
 
T60 Toxic effect of pesticides
 
X60-X84 intentional self harm

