5.2 SAFETY ENDPOINTS

Adverse outcomes are primary endpoints in this study and they include the following categories defined by KCD-7 diagnosis codes and/or NHI procedure codes appearing in medical claims data after the index date.

- GI bleeding
I850, I983, K2211, K226, K228, K250, K252, K254, K256, K260, K262, K264, K266, K270, K272, K274, K276, K280, K282, K284, K286, K290, K3181, K5521, K625, K920, K921, K922
- Fractures
S02, S12, S22, S32, S42, S52, S62, S72, S82, S92, T02, T08, T10, T12, T14.2
- Falls
W00-W19
- Intracranial hemorrhage
I60, I61, I62, I690, I691, I692, S064, S065, S066, S068
- Suicide attempt, self-harm
T40 Poisoning by narcotics and psychodysleptics [hallucinogens]
T41 Poisoning by anaesthetics and therapeutic gases
T42 Poisoning by antiepileptic, sedative-hypnotic and antiparkinsonism drugs
T43 Poisoning by psychotropic drugs, not elsewhere classified
T54 Toxic effect of corrosive substances
T60 Toxic effect of pesticides
X60-X84 intentional self-harm
- Myocardial infarction
I21.9, I21.4, I21.0, I21.1, I21.2, I21.3, I22.0A, I22.0B, I22.0C, I22.8A, I22.8B, I22.8C, I22.8D, I22.8E, I22.8F, I22.8G, I22.8H, I22.8I, I22.8, I22.9, I22.1A, I22.1B, I22.1C
- Epilepsy/seizures
G40.XX
- Stroke
 - Transient ischemic attack
G459, I63, I693
 - Hemorrhagic stroke
I60, I61, I62, I690, I691, I692
 - Ischemic stroke
I63

[NOTE] Hospitalization and CT or MRI codes such as brain CT or MRI procedure code for ischemic stroke and hemorrhagic stroke, or any CT or MRI for systemic embolism are also required for identification.

- Brain CT
HA441, HA451, HA461, HA471, HA851
- Brain MRI
HE101, HE102, HE135, HE201, HE202, HE235, HE301, HE302, HE401, HE402, HE501, HE502, HE535
- Any CT or MRI or CT

HA401-HA416, HA424, HA425, HA434, HA435, HA443-HA449, HA453, HA456-HA459, HA463-HA469, HA473-HA479, HA496, HA497, HA801, HA805, HA809, HA813, HA834, HA835, HA853, HA856, HA857-HA859, S852

- MRI
HE103-HE142, HE203-HE234, HE236-HE241, HE303-HE334, HE403-HE434, HE430-HE434, HE503-HE534, HE536-HE541, HF101, HF102, HF104-HF107, HF201, HF202, HF305, HF306
- Hyponatremia
Will be identified by prescription codes for vasopressin receptor antagonists such as tolvaptan (drug code=616501ATB)

CC
I

[figure not shown]

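### Adherence, a dispensing-based primary endpoint, is also lowered by safety events over a period of undefined length, and the shared self-harm codes can build in part of the recurrence-compliance association

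*SAP*

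**What the plan says.** SAP 5.1 names compliance (persistence, discontinuation, adherence) and recurrence as its main primary effectiveness endpoints. Adherence rests on dispensing claims: "MPR ≥ 0.75 and persistence ≥ 90 will be considered as adherence". The MPR numerator is "Days of medication possession from the prescriptions filled in the 180 days", and the denominator is 180 days plus any surplus supply from the last fill.

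A starred note under adherence then says "For those period with any identified adverse outcome such as GI bleeding will be considered as a non-adherent period". SAP Table 3 (section 5.4) has the same note: "For those period with any identified adverse outcome such as GI bleeding will be considered as non-adherent period". So does the Adherence row of protocol Table 3 (section 9.3), which begins "For those period with any identified adverse outcome such as GI bleeding will be considered as" and ends the same way. The rule therefore did not enter with the SAP. Neither document gives a reason for it.

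Recurrence item 5 in SAP 5.1 is "Suicide attempt identified by the following KCD-7 codes". SAP 5.2, which makes adverse outcomes primary endpoints in their own right, lists "Suicide attempt, self-harm" among them. Primary objective 2 (SAP 2.2) includes the relationship between recurrence and compliance, and SAP 7.2.2 lists recurrence by compliance among its primary-analysis endpoints.

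**The concern.** MPR and persistence are meant to show whether patients kept obtaining their drug. The starred rule makes the result depend on something else: whether a bleed, fracture, fall, stroke, self-harm or other listed claim occurred. This affects two primary comparisons.

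- **Between drugs.** Two drugs with identical dispensing could differ in scored adherence because their users differ in adverse outcomes. Those outcomes are already reported separately, so the adherence result would no longer be a distinct piece of information.
- **Recurrence against compliance.** A self-harm claim counts as a recurrence and also marks its own period as non-adherent. Some of any observed link between poor adherence and recurrence would then come from the scoring and not from patients' behaviour.

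The rule also cannot be programmed as written. Its period could be a claim day, a hospital stay, a prescription interval or the whole window, and two analysts could reach different primary results from the same data.

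**Working it through.** The documents state no sample size, event rate or effect tied to this rule, so there is no plan figure to reproduce. The check compares the definitions and then shows the arithmetic under labelled assumptions.

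**1. When the rule changes anything.** If treatment stops after an event, possession days fall and MPR falls without the rule. Only days on which the patient still holds drug can be recoded from adherent to non-adherent. The rule therefore works in one direction, downward. The text does not say that it alters the persistence component.

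**2. Shared codes.** Recurrence item 5 (SAP 5.1) uses T40, T41, T42, T43, T54, T60 and X60-X84. The self-harm safety endpoint (SAP 5.2) uses the same list. One claim is thus a recurrence, a primary adverse outcome and the trigger for a non-adherent period.

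**3. Window overlap.** The adherence item says "adherence will be measured by MPR and persistence during the first 90 day and 180 day from the index date, respectively", which puts MPR on 90 days, while the MPR item uses 180 days. The analysis in SAP 7.2.2 covers patients who go beyond day 90.
- MPR over 90 days: a self-harm claim after day 90 cannot change it. Overlap remains only for recurrence in the acute phase, which SAP 5.1 also defines.
- MPR over 180 days: claims on days 91 to 180 count towards both recurrence and measured adherence.

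**4. Recoded days needed to cross the threshold.** Assumptions: event days are subtracted from possession days, and there is no extra supply. Find the smallest d with (MPR × W − d)/W < 0.75.

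| Starting MPR | W = 90 | W = 180 |
|---|---|---|
| 1.00 | 23 (67/90 = 0.744) | 46 (134/180 = 0.744) |
| 0.90 | 14 (81 − 14 = 67) | 28 (162 − 28 = 134) |
| 0.80 | 5 (72 − 5 = 67) | 10 (144 − 10 = 134) |

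The starting values are illustrative. With surplus supply of 14 or 30 days in the 180-day formula, a fully supplied patient needs 49 days (145/194 = 0.747) or 53 days (157/210 = 0.748). If the period is the whole window, one event is enough.

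**5. Association created by the shared codes.** Assumptions: true adherence a is 0.40 or 0.50; recurrence is independent of true adherence; a share s of recurrences are self-harm; a fraction f of those patients are turned non-adherent. The recurrence rate cancels, and the odds ratio of recurrence, non-adherent versus adherent, is

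OR = [1 − a(1 − sf)] / [(1 − a)(1 − sf)].

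For example, a = 0.50 and sf = 0.10 give 0.55/0.45 = 1.22.

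| s | f = 1 | f = 0.5 |
|---|---|---|
| 5% | 1.09-1.11 | 1.04-1.05 |
| 10% | 1.19-1.22 | 1.09-1.11 |
| 20% | 1.42-1.50 | 1.19-1.22 |
| 50% | 2.67-3.00 | 1.56-1.67 |

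Without the rule sf = 0 and OR = 1.00.

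**6. Difference between drugs.** Assumptions: equal true adherence a, adverse-outcome incidence of 2% against 6%, and every event turning the patient non-adherent. The scored difference is a × (0.06 − 0.02), which is 1.6 points at a = 0.40 and 2.0 points at a = 0.50.

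**The case against.** The strongest reply is that the rule recodes a period and not a person. Patient-level adherence is a separate test on MPR and persistence, and a short period would leave most well-supplied patients above 0.75. This stands. A reader might infer that a self-harm recurrence makes the patient non-adherent by definition. The text does not say so, and the day counts above show that many recoded days can be needed.

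Second, differences in baseline risk between drugs are partly handled. Protocol 9.7 plans adherence comparisons on matched as well as raw data. SAP 7.1 plans propensity matching and weighting, with age, CCI and comorbidities among the covariates. This also stands, so it would be too strong to say that drugs given to higher-risk patients must look worse. Matching does not help the raw-data results, events caused by the drug itself, or the shared codes.

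Third, self-harm is one of six recurrence routes in the acute phase and seven afterwards. Its share is unknown, and overlap depends on which MPR window applies. The built-in association may therefore be small.

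Fourth, using one event in two endpoints is not an error in itself, particularly as SAP section 3 sets no hypotheses or decision rules. Agreed. The difficulty arises when one of those endpoints is then analysed against the other.

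Finally, the rule is prespecified in both documents. It is therefore not an SAP departure from the protocol, but that supplies neither a rationale nor a period length.

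**Conclusion.** The point holds in a limited form. The rule mixes a primary safety endpoint into a dispensing-based adherence endpoint, leaves its period undefined, and can only lower measured adherence, and only in patients who still hold drug. Where the adherence and recurrence windows overlap, the identical self-harm codes build part of the planned recurrence-compliance association into the scoring.

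The direction follows from the text, but the size does not. The threshold counts assume subtraction from possession days. The odds ratios, roughly 1.04 to 1.22 if self-harm is 5% to 10% of recurrences, rest on an assumed share, an assumed adherence of 40-50% and an assumed fraction of patients recoded. The documents do not show how many patients would change status. The rule should be changed because it affects primary endpoints and a primary objective, and the repair is small.

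**What to change.** - Remove the starred rule from the primary adherence definition in SAP 5.1 item 4, SAP Table 3 and protocol Table 3. Compute MPR and persistence from dispensing claims only.
- Keep the event-adjusted version as a labelled sensitivity analysis. State the length of the period and how it enters the MPR formula.
- Do not use the event-adjusted version in the recurrence-compliance analysis.
- SAP section 1 records that the current amendment was made while data were being analysed. Date this change, document it and report both versions.

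The cost is wording in two documents and one extra run. The downside is a late change to a primary endpoint definition, which dating the change and reporting both versions makes transparent.
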